2.6 Analysis of the key secondary objective

Not Applicable.

2.7 Analysis of secondary efficacy objective(s)

Refer to Table 1.2-1 of Section 1 for the list of secondary objectives.

2.7.1 Secondary endpoints

The analyses of all secondary efficacy endpoints will be based on the ITT.

Refer to Table 1.2-1 of Section 1 for the list of secondary endpoints.

2.7.2 Statistical hypothesis, model, and method of analysis

PASI

Summary statistics for PASI 50, PASI 75, PASI 90, PASI 100 response by visit will be presented with absolute and relative frequencies. Confidence intervals for response rates will be derived as well, based on the score method including continuity correction (Newcombe 1998). The summaries will be done using prevalence (observed data), LOCF and NRI approaches.

Summary statistics will be provided for absolute PASI scores and for percent changes from baseline by visit and cohort using prevalence, and LOCF approches. Graphical representations will also be provided on ITT set.

The two cohorts will be compared on PASI scores (absolute change from baseline) using MRMM model with LOCF, prevalence and MI approaches on ITT set.

PASI Changes vs baseline: Linear Mixed Model for Repeated Mesurements (MMRM):

In order to evaluate if there is a differences between cohorts in PASI changes at each time point vs week 0, a longitudinal analyses of changes from baseline will be performed over the course of the study including all the measurements assessed at each time point for the ITT population using a linear mixed model for repeated measurements (MMRM). An unstructured

covariance matrix for the repeated measures within each patient will be applied in the analysis, if the model does not converge, compound symmetry will be used. The explanatory variables in the longitudinal model include cohort, visit, cohort-by-visit interaction, missing data pattern (completers, missing one assessments, missing two assessments, missing three assessments, etc till all visits in the overall study period), propensity score, and corresponding baseline (week 0). The two cohorts will be compared at each time point by reporting a point estimate, p-value, and 95% confidence interval for the treatment difference, based on least squares means.

The propensity score analysis will consider the following baseline factors: age, geographical region (i.e. north vs south vs central), BMI categories (<25 vs >=25), waist circumference, smoking status (Yes vs No), metabolic syndrome (yes vs no), previous PsO therapy (naïve vs previous systemic therapy vs previous biologic therapy), PsA (yes vs no), age at diagnosis of psoriasis, IGA mod 2011 (severe, moderate, mild) as strata factors. This approach allows us also to maximize the analysis model adding only one variable instead of several ones.

The choice of the MMRM model instead of a simple ANCOVA model on changes vs week 0 considering the prevalence approach or Last observation carried forward (LOCF) approach was done because the LOCF approach would underestimate the within-group mean changes between treatments compared with MMRM, whereas the prevalence approach tend to overestimate the within-group changes (Prakash et al. 2008).

In addition to that, similar MMRM model will be fitted on LOCF and prevalence set without the propensity score approach. An unstructured covariance matrix for the repeated measures within each patient will be applied in the analysis, if the model does not converge, compound symmetry will be used. The explanatory variables in the longitudinal model include cohort, visit, cohort-by-visit interaction, age, geographical region (i.e. north vs south vs central), BMI categories (<25 vs >=25), waist circumference, smoking status, metabolic syndrome (yes vs no), age at diagnosis of psoriasis, and along with interaction terms of each factor with visit.

The SAS codes are described in appendix section.

MMRM with MI approach

MMRM analysis will be also performed using multiple imputation (MI) approach on ITT population.

The multiple imputation will be done with pattern-mixture models (PMMs) as above, that allows formulating assumptions regarding missing data in a transparent and clinically interpretable manner.

The SAS codes are described in appendix section.

PASI 75

A logistic regression analysis model will be also fitted, considering age, geographical region, BMI, smoking status, metabolic syndrome, TNF α -308 polymorphism (if feasible), as well as all clinical relevant variable resulting statistically different at baseline between cohort, as strata factors. The analyses will be done similar to primary analyses based on prevalence, LOCF and NRI approaches using ITT set.

Time to reach PASI 90

The differences between cohorts Cw6-negative and Cw6-positive in time to reach PASI 90 will be evaluated by means of a log-rank test. The hazard ratios and their corresponding 95% confidence intervals will be also computed using a stratified Cox proportional hazards regression model with Cw6 group and baseline PASI as explanatory variable and stratified by geographical region and BMI categories, as well as age categories (tertiles).

The Kaplan-Meier estimates of the cumulative rate for each cohort will be plotted, together with p-value. Median time to reach PASI will be also be provided.

Time to reach PASI 75

The differences between cohorts Cw6-negative and Cw6-positive in time to reach PASI 75 will be evaluated by means of a log-rank test. The hazard ratios and their corresponding 95% confidence intervals will be also computed using a stratified Cox proportional hazards regression model with Cw6 group and baseline PASI as explanatory variable and stratified by geographical region and BMI categories, as well as age categories (tertiles).

The Kaplan-Meier estimates of the cumulative rate for each cohort will be plotted, together with p-value. Median time to reach PASI will be also provided.

IGA mod 2011

Summary statistics for the IGA mod 2011 score over time, as well as percent change from baseline, will be presented by visit and cohort.

Changes from baseline between cohorts will be compared using linear mixed model for repeated measurements (with the same covariates used in MMRM model on PASI) on LOCF and prevalence approach.

Summary statistics for IGA 0 or 1 response by visit and cohort will be presented with absolute and relative frequencies. Differences between cohorts at each time point will be explored by means of a logistic regression model adjusting considering age, geographical region (i.e. north vs south vs central), BMI categories (<25 vs >=25), weight, waist circumference, smoking status (Yes vs No), metabolic syndrome (yes vs no), previous PsO therapy (naïve vs previous systemic therapy vs previous biologic therapy), PsA (yes vs no), age at diagnosis of psoriasis, TNF α -308 polymorphism, IGA mod 2011 (severe, moderate, mild) as strata factors for LOCF, NRI and prevalence approach. Similar model selection techniques will be used.

Patient is considered as IGA 0 or 1 responder if the patient achieves a score of 0 or 1 and improved by at least 2 points on the IGA scale compared to baseline.

Dermatology Life Quality Index

Please refer to section 2.11

Hospital Anxiety and Depression Scale

Please refer to section 2.11

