6.4 Efficacy

6.4.1 Psoriasis Area and Severity Index (PASI)

The primary efficacy variable is the measurement of the severity of psoriasis using the Psoriasis Area and Severity Index (PASI) ([Richard GB et al. 2013](#)), the most widely used tool for this purpose. PASI combines the assessment of the severity of lesions and the area affected into a single score with a range of 0 (no disease) to 72 (maximal disease). The PASI will be assessed at each visit from V2 to V12 of the core study and at all four visits of the extension period.

A PASI score ([Weisman et al. 2003](#)) will be calculated as indicated in [Appendix 3](#). The head, trunk, upper limbs and lower limbs are assessed separately for erythema, thickening (plaque elevation, induration), and scaling (desquamation). The average degree of severity of each sign in each of the four body regions is assigned a score of 0-4. The area covered by lesions

on each body region is estimated as a percentage of the total area of that particular body region. In particular:

1. The neck is assessed as part of the head.
2. The axillae and groin are assessed as part of the trunk.
3. The buttocks are assessed as part of the lower limbs.
4. When scoring the severity of erythema, scales should not be removed.

Because the head and neck, upper limbs, trunk and lower limbs correspond to approximately 10%, 20%, 30% and 40% of the body surface area, respectively, the PASI score is calculated using the formula:

$$\text{PASI} = 0.1(\text{EH}+\text{IH}+\text{DH})\text{AH} + 0.2(\text{EU}+\text{IU}+\text{DU})\text{AU} + 0.3(\text{ET}+\text{IT}+\text{DT})\text{AT} + 0.4(\text{EL}+\text{IL}+\text{DL})\text{AL}$$

Usually, a PASI 75 improvement is used as a minimum threshold to evaluate the clinical efficacy of new psoriasis treatments (Callen JP et al. 2003). A PASI 90 improvement will be used as primary endpoint in this study.

The following definitions of PASI will be used in this study:

- PASI 50 response: subjects achieving $\geq 50\%$ improvement (reduction) in PASI score compared to baseline are defined as PASI 50 responders.
- PASI 75 response: subjects achieving $\geq 75\%$ improvement (reduction) in PASI score compared to baseline are defined as PASI 75 responders.
- PASI 90 response: subjects achieving $\geq 90\%$ improvement (reduction) in PASI score compared to baseline are defined as PASI 90 responders.
- PASI 100 response / remission: complete clearing of psoriasis (PASI=0).

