5.4.3 Secondary analysis

The SAS procedure PROC FREQ with Method= NEWCOMBE option, will be used to derive Confidence intervals for response rates with the following sample SAS code:

PROC FREQ DATA = \dots ;

BY visit;

TABLES trtan*resp / riskdiff (column=2 cl=(NEWCOMBE));

RUN;

The SAS procedure PROC MIXED will be used for linear mixed model for repeated measurements (MMRM) analysis with the following sample SAS code:

PROC MIXED DATA=dataset noclprint;

CLASS cohort vis1n usubjid MissingPattern;

MODEL Changes= cohort week0 dropout visit prop_score

cohort*visit cohort*MissingPattern;

REPEATED visit/subject=usubjid TYPE=cs;

LSMEANS cohort*visit/pdiff cl;

RUN;

The SAS procedure PROC PHREG, will be used to perform computed using a stratified Cox proportional hazards regression model with Cw6 group and baseline PASI as explanatory variable with the following sample SAS code:

PROC PHREG DATA=....;

CLASS trtpn baseline ..;

MODEL var*censor(0)= trtpn base.../rl ties=efron ;

RUN;

The SAS procedure PROC LIFETEST, will be used to perform log-rank test and to plot Kaplan-Meier estimates of the cumulative rate for each cohort with the following sample SAS code:

PROC LIFETEST DATA=... PLOT;

TIME timevar*censor(0);

STRATA ...;

RUN;

The SAS procedure PROC CORR, will be used to perform Spearman's (or Pearson's product moment correlation depending on data distribution) correlation with the following sample SAS code:

PROC CORR DATA = pearson/spearman OUTP=CORR;

VAR VAR1 VAR2;

RUN;

The SAS procedure PROC UNIVARIATE with NORMAL option, will be used to check the normality with the following sample SAS code:

PROC UNIVARIATE DATA = normal;

VAR var.../options...;

CLASS var;

RUN;

The SAS procedure PROC UNIVARIATE, will be used to perform Wilcoxon signed rank test with the following sample SAS code:

PROC UNIVARIATE DATA =;

VAR var...;

RUN;

The SAS procedure PROC TTEST, will be used to perform paired t-test with the following sample SAS code:

PROC TTEST;

PAIRED VARbefore*VARafter;

RUN;

The SAS procedure PROC FREQ with EXACT statement equal to MCNEM or AGREE will be used to perform Mc Nemar's test with the following sample SAS code:

PROC FREQ DATA =;

TABLES trtan*resp;

EXACT MCNEM or AGREE;

RUN;

SAS code for poisson regression model

proc genmod data=demo_ae ;

class cw6 sex age_group/ param = glm;

model numev = cw6 age_group sex / type3 dist=poisson;

lsmeans cw6 /ilink cl diff;

lsmeans age_group /ilink cl diff;

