lsmeans sex /ilink cl diff;

run;

proc genmod data=demo_ae ; class cw6 (param = ref ref = "NEGATIVE") sex (param = ref ref = "M") age_group (param = ref ref = "<=40 years"); model numev = cw6 age_group sex / type3 dist=poisson ; estimate "IRR Cw6 (POS vs NEG) " cw6 1 -1; estimate "IRR Age (>40 vs <=40)" age_group 1 -1; estimate "IRR Sex (Female vs Male)" sex 1 -1;

run;

PASI Changes vs baseline: Linear Mixed Model for Repeated Mesurements (MMRM):

The SAS procedure PROC MIXED will be used in the analysis, in particular:

proc mixed data=dataset noclprint;

class cohort vis1n usubjid MissingPattern;

model Changes= cohort week0 dropout visit prop_score

cohort*visit cohort*MissingPattern;

repeated visit/subject=usubjid type=un;

lsmeans cohort*visit/pdiff cl;

run;

where changes includes all changes vs week 0 of PASI; the dropout variable is the missing pattern (i.e. a categorical variable with values of 1, 2, 3 etc.. representing completers, 1 assessment missing, 2 assessments missing, 3 assessment missing etc. in considered dependent variable –e.g. PASI); the prop_score variable is the propensity score. In order to take all the confounding factors into account, the propensity score methodology will be applied and will be included in the final model, as described above. Propensity score will be derived using logistic regression model considering cohort as the dependent variable and baseline covariates as the factors in the model. The derived propensity score will be used as the covariate in the MMRM model.

MMRM with MI approach

Multiple imputation will be performed in SAS using the following three-stage approach:

PROC MI will be applied for each PASI change (or each post baseline PASI score) containing some missing values, which results in creation of multiple copies of this dataset. All copies contain identical values of the non-missing data items, but different values imputed for missing items. The following SAS statement will be used:

proc mi data=PASI_in out=PASI_out seed=1425;

var cohort Baseline PASI score PASI score at week 1 PASI score at week 2 PASI score at week 3 PASI score at week 4 PASI score at week 8 PASI score at week 12 PASI score at week 16 PASI score at week 20 PASI score at week 24;

class cohort;

monotone regression;

run;

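### The SAP's only fallback for the PASI mixed models is compound symmetry, and its printed programs disagree on the structure; wherever compound symmetry is used, the per-visit intervals and p-values will be wrong.

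*SAP*

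**What the plan says.** SAP 2.7.2 describes two mixed models for PASI change from baseline.

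- The first adjusts for baseline PASI, a propensity score and missing-data pattern. The second, for the LOCF and observed-data sets, drops the propensity score and lists individual covariates with their visit interactions. Baseline PASI is not in that second list.
- Both paragraphs carry the same covariance rule: "An unstructured covariance matrix for the repeated measures within each patient will be applied in the analysis". Each then gives one fallback and names no structure in between: "if the model does not converge, compound symmetry will be used".
- The purpose is inference visit by visit: "The two cohorts will be compared at each time point by reporting a point estimate, p-value, and 95% confidence interval for the treatment difference".

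SAP 5.4.3 prints two programs.

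- The first is introduced generally: "The SAS procedure PROC MIXED will be used for linear mixed model for repeated measurements (MMRM) analysis with the following sample SAS code". It contains "REPEATED visit/subject=usubjid TYPE=cs".
- The second, under the PASI change heading, contains "repeated visit/subject=usubjid type=un".
- Neither has an EMPIRICAL option.

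For IGA, SAP 2.7.2 specifies a "linear mixed model for repeated measurements (with the same covariates used in MMRM model on PASI) on LOCF and prevalence approach". That carries over covariates but is silent on covariance.

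The number of repeated measures follows from the visit schedule in section 6.4.1 of the protocol, which reads: "The PASI will be assessed at each visit from V2 to V12 of the core study and at all four visits of the extension period".

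**The concern.** Compound symmetry has two parameters. It assumes the same residual variance at every visit, and the same correlation between weeks 1 and 2 as between weeks 1 and 72. The sample size section expects PASI 90 rates of 71% to 80% at week 16, so most patients move from active disease to near clearance within the series. Residual spread is unlikely to stay constant through that.

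Under compound symmetry, the standard error at each visit comes from a variance pooled over all visits. It is too small where the true variance is above the pool and too large where it is below. The error therefore falls on the per-visit p-values and intervals that the model is meant to supply. Whether Cw6 alters the kinetics of response is a stated purpose of the extension.

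Separately, because the two programs differ in covariance type and IGA has no stated structure, two programmers could follow this SAP and report different standard errors.

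**Working it through.** **1. The plan's own figures.** The documents give no SD, power or precision for the mixed models, so there is nothing of that kind to reproduce. The sizes come from the PASI 90 calculation (Protocol 9.7), which does reproduce. With 80% in both cohorts, a 12-point margin and 219 + 146 patients, SE = √(0.16/219 + 0.16/146) = 0.0427, and power = Φ(0.12/0.0427 − 1.96) ≈ 80%.

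**2. Parameter count.** There are 9 core visits after baseline (weeks 1, 2, 3, 4, 8, 12, 16, 20, 24) and 4 in the extension (weeks 36, 48, 60, 72), 13 in all.

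- Unstructured: 13 × 14 / 2 = 91 parameters (14 × 15 / 2 = 105 if E0 is a separate visit).
- Heterogeneous compound symmetry: 13 + 1 = 14.
- Compound symmetry: 2.

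**3. Formula.** With complete balanced data, the ratio of the compound-symmetry standard error to the true one at visit v is r = √(mean of the 13 visit variances) / SD at v. Actual two-sided type I error is 2 × [1 − Φ(1.96 r)]. Equal SDs give r = 1 and 5%.

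**4. Model with a common baseline term.** Assumed residual SDs are 5, 2.5 and 2.2 at weeks 1, 16 and 72, with the other visits interpolated linearly in time or in log time.

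- Linear: sum of squares 154.66, pooled SD √(154.66/13) = 3.449.
- Log time: sum of squares 130.30, pooled SD √(130.30/13) = 3.166.

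| Week | r, linear | Type I error | r, log time | Type I error |
|---|---|---|---|---|
| 1 | 3.449/5 = 0.69 | 17.6% | 3.166/5 = 0.63 | 21.5% |
| 16 | 3.449/2.5 = 1.38 | 0.7% | 3.166/2.5 = 1.27 | 1.3% |
| 72 | 3.449/2.2 = 1.57 | 0.2% | 3.166/2.2 = 1.44 | 0.5% |

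A milder assumed fall (4, 3, 2.9) gives 10-11%, 2.9-3.4% and 2.4-2.9%.

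**5. Model without baseline PASI (the second covariate list).** Once patients are nearly clear, change is close to minus the baseline score, so its spread approaches that of baseline and grows with time. The illustration assumes mean baseline PASI 18 with coefficient of variation 0.45 (SD 18 × 0.45 = 8.1), mean week-1 improvement of about 12% to 32%, and 80% at PASI 90 by week 16.

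- SD of change is 1.95 to 4.04 at week 1 and about 7.7 from week 16. The pooled SD is 6.81 to 6.92.
- Week 1: r = 6.81/1.95 = 3.5 down to 6.92/4.04 = 1.7 (2.2 in the middle case), so type I error is below 0.1%.
- Weeks 16-72: r = 0.88 to 0.90, type I error about 8%.

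Adding one common baseline slope to the same illustration turns the direction round: r = 0.60 to 0.64 at week 1 (21-24%) and 1.45 to 1.50 at weeks 16-72 (about 0.4%). This agrees with step 4.

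**6. Simulation check.** There were 600 replicates, with 219 and 146 patients, 13 visits, 306 patients with weeks 36-72, and correlation 0.6.

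- Equal SDs: type I error 4.2-5.7% under compound symmetry.
- SD doubling between weeks 1 and 16: r = 1.71 at week 1 (0.3%) and 0.84-0.89 at weeks 16, 24 and 72 (9-10%).
- Visit-specific variances instead: 4.2-6.7% across SD ratios of 1 to 3 (Monte Carlo standard error about 0.9 points).

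**The case against.** - **The governing text puts unstructured first, twice.** The first program is labelled as sample code and could be read as the fallback printed beside the first choice. It would not run as printed, because its CLASS statement lists vis1n while REPEATED uses visit. A reader might infer that the plan starts with compound symmetry; the text does not support that. What stands is that the general program conflicts with the text and is not marked as a fallback.
- **Convergence failure is not shown to be likely.** A reader might infer it from 91 parameters, but about 365 × 9 + 306 × 4 ≈ 4,500 observations are planned and LOCF makes one dataset nearly complete. In 12 simulated datasets with dropout and 2% intermittent missingness, an unstructured maximum-likelihood fit converged every time. That check was not PROC MIXED and left out the missing-pattern terms, so it does not exclude failure. The second model also interacts every covariate with visit.
- **The direction is not uniform.** A reader might infer that early intervals are always too narrow and late ones too wide. That holds only with baseline in the model. If baseline was meant to carry over to the second model, the SAP should list it.
- **IGA is an inference.** Only the covariates are carried over, so a fallback for IGA cannot be read from the text. The gap is the missing statement.
- **Impact is limited.** Mean PASI change is not a listed objective (mean IGA change is). Kinetics are also addressed by time to PASI 75 and PASI 90 and by responder rates at each visit. The printed multiple-imputation code fits ANCOVA separately by visit, so it does not pool variances.

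**Conclusion.** The point holds in a conditional form and is minor. If compound symmetry is used, through the fallback or by running the general program's structure, the per-visit standard errors rest on one pooled variance and the p-values and 95% intervals are wrong unless the variances really are equal. Under the assumed SDs, the baseline-adjusted model rejects about four times too often at week 1 and far too seldom from week 16. The model without baseline is far too conservative at week 1 and rejects about 8% of the time at weeks 16-72.

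Both size and direction rest on assumptions, because the documents report no SD at any visit and nothing was computed for IGA. There is no error if unstructured is fitted. The primary PASI 90 comparison, the sample size and the by-visit imputation analysis do not depend on this. The mismatch between the programs, and the silence on IGA, need correcting in any case.

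**What to change.** - In SAP 5.4.3, print type=un in the general MMRM program so that it agrees with the text and with the PASI program.
- In SAP 2.7.2, state that the IGA model follows the same covariance rule as PASI.
- In both MMRM paragraphs of 2.7.2, replace the compound symmetry fallback with a structure that has visit-specific variances, for example heterogeneous compound symmetry (CSH), and require EMPIRICAL (sandwich) standard errors whenever unstructured is not used. Structures that tie correlation to visit order are less suitable here, because visits are 1, 4 and 12 weeks apart.

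The cost is SAP wording and code only, with no new data, visits or patients. The downside is slightly less efficient estimates if the fallback is reached.

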where variables PASI score at week 1 PASI score at week 2 PASI score at week 3... PASI score at week 24 contain missing values for some patients at each PASI time point, which PROC MI will impute using linear regression models.

Then we can calculate changes vs. baseline at each time point

```
data PASI in out1;
```

set PASI_out;

visit="Week 1"; change= PASI score at week 1 – Baseline PASI score; output;

visit="Week 2"; change= PASI score at week 2 - Baseline PASI score; output;...

visit="Week 24"; change= PASI score at week 24 - Baseline PASI score; output; run;

and then we will perform the ANCOVA model using the following statement:

```
proc mixed data= PASI_in_out1;
by visit;
class <As required factors >;
model change =<As per reqired covarites> /;
lsmeans treatment /diff pdiff cl;
ods output diffs=diff_MI lsmeans=LSM_MI;
run;
```

where prop_score is the same continuous variable used for the primary model.

Results of the ANCOVA analysis on 500 imputed dataset will be combined to derive an overall results using the following code:

proc mianalyze parms(classvar=full)=diff_mi;

class cohort;

modeleffects cohort:

ods output parameterestimates=DIFF_MIAN;

by visit;

run;

proc mianalyze data=lsm_mi;

class cohort;

modeleffects cohort:

ods output parameterestimates=LSM_MIAN;

by visit;

run;

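### The main PASI mixed model holds the effects of week-0 PASI and the propensity score constant over visits, so a baseline PASI difference between the Cw6 cohorts would bias the visit-specific comparisons, usually most at early visits

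*SAP*

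**What the plan says.** SAP 2.7.2, under PASI changes versus baseline, models absolute change in PASI over all visits in the ITT population. The terms are cohort, visit, cohort-by-visit, missing-data pattern, "propensity score, and corresponding baseline (week 0" value. Only cohort is crossed with visit. Both PROC MIXED programs in SAP 5.4.3 agree: the statement reads "model Changes= cohort week0 dropout visit prop_score" and continues with cohort-by-visit and cohort-by-missing-pattern terms only.

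The result is read visit by visit: "The two cohorts will be compared at each time point by reporting a point estimate, p-value, and 95% confidence interval". The covariance is unstructured, but "if the model does not converge, compound symmetry will be used"; one printed program uses each form.

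Three neighbouring analyses bear on the point:
- A further mixed model for the LOCF and observed data, without the propensity score, lists its factors "and along with interaction terms of each factor with visit". Week-0 PASI is not among those factors.
- In the multiple-imputation program, changes are computed per visit and "then we will perform the ANCOVA model using the following statement", run by visit with placeholder covariates.
- The IGA model is fitted "with the same covariates used in MMRM model on PASI", without saying which PASI model is meant.

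**The concern.** PASI cannot fall below 0, and the sample-size section expects 71% of patients to reach PASI 90 at week 16. As patients approach clearance, absolute change approaches minus the baseline value. The slope of change on baseline therefore moves from shallow in the first weeks towards -1. A single slope is a compromise that is wrong at some visits.

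In a randomised trial this would mostly cost precision. Here the cohorts are defined by Cw6 status, and SAP 2.3.2 itself plans to test whether baseline PASI is balanced between them. The propensity score does not repair the problem: its factor list omits baseline PASI, and it too enters with one constant effect. Any baseline gap is multiplied by the slope error at each visit and appears as a cohort difference that changes over time, which could be mistaken for a genotype effect on the course of response.

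**Working it through.** **Plan's own figures.** The documents give none for this model. The cohort sizes used below come from the sample-size section and reproduce. With 80% response in both cohorts (equal rates are what reproduce the N) and a 0.12 margin, the standard error is √(0.16 × (1/219 + 1/146)) = 0.0427. Then 0.12/0.0427 − 1.96 = 0.85, which is 80.2% power with 219 + 146 = 365; 365/0.9 gives 406.

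**Formulas.** Let s_v be the true slope of change on baseline at visit v, b the fitted common slope, and D the difference in mean baseline PASI (positive minus negative).
- Bias at visit v = (s_v − b) × D.
- SE ratio at visit v = √(1 + (s_v − b)² × Var(baseline)/residual variance at v).

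**Assumptions not in the documents.** Both set-ups have no cohort effect given baseline and complete data, and omit the propensity score and missing pattern.
- Set-up A: baseline PASI mean 20, SD 9; 13 post-baseline visits; improvement 12–28% at week 1 and 85–95% at week 16, across fast, mid and slow profiles.
- Set-up B: mean 20, SD 6; nine visits to week 24; mean improvement 20% at week 1 rising to 90% at week 16, capped at 100%; between-/within-patient SD of 12/8 or 18/10 percentage points.

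**Bias and false positives at D = 2** (two-sided 5% tests):

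| Setting | s at wk 1 | s at wk 16 | b | Wk 1: formula | Wk 1: simulated | Wk 16: formula | Wk 16: simulated |
|---|---|---|---|---|---|---|---|
| A mid, unstructured | −0.22 | −0.88 | −0.85 | 0.63 × 2 = 1.26 | +1.25 (44%) | −0.03 × 2 = −0.06 | −0.07 (7%) |
| A slow, unstructured | −0.16 | −0.81 | −0.54 | 0.38 × 2 = 0.76 | +0.76 (36%) | −0.27 × 2 = −0.54 | −0.56 (24%) |
| A mid, compound symmetry | −0.22 | −0.88 | −0.73 | 0.51 × 2 = 1.02 | +1.02 (65%) | −0.15 × 2 = −0.30 | −0.29 (5%) |
| B, unstructured | −0.20 | −0.87 | −0.99 to −1.05 | 1.58 to 1.70 | 1.5 to 1.7 (66–71%) | 0.24 to 0.36 | 0.2 to 0.4 (11–15%) |

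In A mid (unstructured), bias fades from +0.94 at week 2 (29%) to +0.48 at week 4 (14%). Week-1 rejection is 14% for D = 1 and 75% for D = 3. In A slow, week 24 has −0.61 (28%). With D = 0 there is no bias and error is nominal.

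**How large might D be?** Chance alone gives an SD of 9 × √(1/219 + 1/146) = 0.96 points, or 0.64 with SD 6. Two points is thus about 2.1 or 3.1 chance SDs. A genotype-related difference would add to this, but the documents give no figure for one.

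**Precision.** In A mid (unstructured), the week-1 SE is 0.71 with the common slope and 0.38 with visit-specific slopes, a ratio of 1.87; at week 16 both are about 0.26. In A slow the ratios are 0.48/0.31 = 1.55 at week 1 and 0.44/0.34 = 1.29 at week 16. In B the week-16 SEs are 0.27 against 0.26 and 0.36 against 0.34. Applying the SE formula over a grid of residual structures gives late-visit inflation of 4–36%, and week-1 ratios from 1.59 to 2.85.

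**After adding baseline-by-visit** (unstructured, D = 2): in A mid, bias is 0.00 to −0.01 and rejection 3.9–4.9% at the visits shown. In A slow rejection is 3.9–6.0%. In B it is roughly 5% at every visit.

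**The case against.** The strongest reply is that this is a secondary model, that the bias is conditional, and that the plan has safeguards. Much of that stands. Table 1.2-1 lists response rates by visit, time to PASI 75 and 90, and IGA change; absolute PASI change is not a listed endpoint. The Cox models carry baseline PASI as a covariate. Without a baseline gap nothing is biased, and the planned homogeneity test would make a gap visible. The multiple-imputation ANCOVA is run by visit, so whatever covariates it carries have visit-specific slopes. But its printed covariates are placeholders, and seeing an imbalance does not correct the main model's estimates.

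Four stronger readings are tempting and are not supported:
- **That the damage falls mainly on week 16 and later.** This would need the common slope to sit near the early slopes. In set-ups A mid and B it sits near or beyond the late ones. Only the slow profile gives late bias approaching the early bias. Other residual structures could shift this.
- **That the question about Cw6 and response kinetics is compromised.** The planned time-to-response and response-rate analyses do not use this model.
- **That the SAP's additional mixed model already has the right form.** It includes terms "along with interaction terms of each factor with visit", which shows the principle is accepted, but week-0 PASI is not a listed factor.
- **That the IGA model has the same flaw.** It is planned for LOCF and observed data, the settings of the additional model, so it may reuse that covariate list instead.

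**Conclusion.** The point holds for the main PASI mixed model. The missing terms are certain from the text and both programs, and the direction of the problem is algebraic: slopes that steepen over time cannot share one coefficient. Size and location rest on assumed baseline values, response profiles and residual structure. With an unstructured covariance and a 2-point gap, week 1 is off by about 1.2–1.7 PASI points with 44–71% false positives in the mid-speed case of A and in B, and by 0.76 points (36%) with slow response. Week 16 is off by about 0.1–0.6 points with 7–24% false positives. Precision loss is also mainly early: about 55–90% at week 1 in simulation, against 0–36% at late visits.

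The propensity-score half rests on the same algebra, applies only if that score's effect changes over visits, and was not quantified. The primary week-16 PASI 90 comparison does not depend on any of this. The change is worth making because the model reports a p-value at every visit and the remedy is nearly free.

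**What to change.** - In SAP 2.7.2, add baseline-by-visit and propensity-score-by-visit to the terms of the main PASI mixed model. In both PROC MIXED programs in SAP 5.4.3, add week0*visit and prop_score*visit to the MODEL statement.
- In the IGA paragraph, name the PASI model whose covariates are reused. If it is the main one, add the same two interactions there.
- In the multiple-imputation program, replace the placeholders with the actual covariates, including week-0 PASI and the propensity score.

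The cost is two model terms and a few sentences. With 13 post-baseline visits, each interaction uses 12 further parameters, 24 in all, which is small against about 365 patients. If the model falls back to compound symmetry, the interactions still remove the bias but do not ensure nominal error: in the slow profile rejection then ranged from 0.9% to 13.6% across the visits shown, because that covariance form did not fit.
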